7.6 Analysis of Efficacy Data

The primary analysis as stated in the protocol is on change in HbA1c, and statistical methodology for measures is planned that follow standard statistical recommendations from regulatory authorities. Additionally, an important key efficacy analysis is the responder analysis, detailed in this SAP. The statistical methodology for the responder analysis is the standard Fisher's exact test.

For completeness, an observed cases analysis will be done by visit in which no data are excluded, no data are imputed, and no data are represented at times other than when they were observed. As an alternative for handling missing data according to the rules of the primary analysis, a supportive analysis will be done using last-observation-carried-forward (LOCF).

For statistical analyses, 95% confidence intervals will be produced for the least squares means (LSM) in each treatment group, as well as the LSM differences as compared to placebo. For MMRM and ANCOVA, two-sided p-values will be displayed for the comparison against placebo.

To ensure robustness of analysis conclusions against parametric assumptions, rank analogues will be executed as supportive analysis. If the PPS differs from the FAS by more than 10%, the analyses will be replicated on the PPS. If the PPS and the FAS do not differ by more than 10%, analysis may not be done on the PPS. Final judgments will be made at the blind data review meeting in accordance with ICH E9.

All analyses will be done using the intent-to-treat (ITT) principle.

7.6.2 Secondary Efficacy

All secondary endpoints will use the FAS.

Categorical endpoints will utilize Fisher's exact test.

Continuous secondary endpoints will be summarized by treatment group and visit. MMRM will also be used to analyze those endpoints.

Statistical methodology for secondary analysis will conform to methodology for primary analysis following the ITT principle and using observed-cases approach and LOCF approach using the last assessment. The Likert-scale QoL question will be dichotomized as "improved quality of life" or "no change in quality of life or worse." Fisher's exact test will be done to compare subjects treated with TTP399 with subjects treated with placebo.

Measurement variables will be analyzed using ANCOVA and ANOVA procedures, using parametric (if warranted) and nonparametric methods. Parametric assumptions will be examined; if parametric assumptions are found to be unwarranted, rank analogues will be advanced.

Secondary efficacy analysis on measures that are continuous will examine drug effects within each treatment group using:

- Paired-t test (1-sample t-test)
- Wilcoxon (1-sample) test.

Within each treatment group, the significance of the percent change from baseline will be assessed using a paired-t test (1-sample t-test). Supportive analysis will be done using a Wilcoxon (1-sample) test.

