8.11. Management of Patients' Glycemic Control and Insulin Dose Adjustments

Patients will be counseled on identification and management of hypoglycemia and hyperglycemia. Glucose levels will be monitored using unblinded continuous glucose monitoring (if patients already have CGM) and self-monitoring of blood glucose using glucometers if unblinded CGM glucose values are not available. **Sentinel** patients are required to have a good hypoglycemic awareness and live with someone who has a good hypoglycemia awareness.

Parts 1 and 2, only

Prior to the placebo run-in period, the PI or designee will determine if the patient's basal insulin dose needs to be optimized to meet the fasting/pre-meal glucose target generally from 80-130mg/dL. If the PI determines that basal insulin dose adjustment is needed, the PI or designee, in collaboration with the patient, will optimize the basal insulin dose for up to 3 weeks prior to the placebo run-in period. If basal insulin dosing is adequate, the patient will move directly into the placebo-run in period. (See Figure 6 below).

Figure 6: Decision Flow Chart for Patient Visits Prior to Randomization

*Adjust basal insulin to target fasting/pre-meal glucose levels generally between 80-130 mg/dL

The PI or designee will use the following guidance in combination with the recent glucose data to instruct the patient on insulin adjustments needed.

BASAL INSULIN DOSE ADJUSTMENT PERIOD (up to 3 weeks before Week -2)

The PI or designee will review the past 14 days of CGM data (Part 1) or fasting/pre-meal glucose levels for the past 7 days using either CGM or glucometer data (Part 2) and determine if a basal insulin dose adjustment period is needed.

If basal insulin adjustments are needed, the basal rate should be assessed and adjusted to target fasting/pre-meal glucose levels generally between 80-130 mg/dL

If Low Blood Glucose: Make immediate insulin adjustment.

If Elevated Blood Glucose: Verify trends 2–3 days before adjusting insulin.

DURING PLACEBO RUN-IN PERIOD (2 weeks prior to randomization)

Do not make insulin adjustments except in response to safety concerns.

Record in the EDC:

- CSII: basal rate, Active Insulin Time and type of Pump, ICF and ICR
- MDI: basal insulin dosing information, ICR and ISF

DURING DOUBLE-BLIND PERIOD:**First day of dosing (Week0/Day 1):**

Reduce bolus insulin:

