INCREASE insulin to carb ratio (ICR, g/U) by 1-3 g/U (10-30%, usually 20%), e.g., if the ICR is 10g/U during run-in period increase the ICR to 11 or 13g/U, usually 12g/U.

And

INCREASE insulin sensitivity factor (ISF) by 10-30%, usually 20%, e.g. if the ISF is 40g/U during run-in period increase the ISF to 44-52% or, usually 48g/U.

Record in the EDC:

- CSII: basal rate, active insulin time, ICF and ICR
- MDI: basal insulin dosing information, ICR and ISF

During the first two weeks of dosing:

Adjust insulin to the following glycemic targets:

- Fasting/pre-meal: 80-130 mg/dL
- Post-meal peak: < 180 mg/dL (post-meal peak < 200mg/dL may be acceptable target at the PI's discretion)

If Low Blood Glucose: Make immediate insulin adjustment.

If Elevated Blood Glucose: Verify trends 2–3 days before adjusting insulin.

The adjustment of bolus insulin should be accomplished by **adjusting ICR and ISF**

Record any adjustments in the EDC:

- CSII: basal rate, active insulin time, ICF and ICR
- MDI: basal insulin dosing information, ICR and ISF

After two weeks of dosing:

Adjust insulin to the following glycemic targets:

- Fasting/pre-meal: 80-130 mg/dL
- Post-meal peak: < 180 mg/dL (post-meal peak < 200mg/dL may be acceptable target at the PI's discretion)

If Low Blood Glucose: Make immediate insulin adjustment.

If Elevated Blood Glucose: Verify trends during patient calls and visits before adjusting insulin.

The adjustment of bolus insulin should be accomplished by **adjusting ICR and ISF**

Record any adjustments in the EDC:

- CSII: basal rate, active insulin time, ICF and ICR
- MDI: basal insulin dosing information, ICR and ISF

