6.1.2 Secondary Efficacy

Secondary variables of analysis include:

- Achievement of no more than trace ketones in urine post-treatment
- Achievement of no treatment-emergent abnormal value in serum BOHB
- Achievement of no more than trace ketones in urine or treatment-emergent abnormal value in BOHB in serum
- Change from baseline relative to:
 - Time in target glycemic range (70-180 mg/dL);
 - Time in hyperglycemic range
 - Level 1 > 180 mg/dL
 - Level 2 > 250mg/dL
 - Time in hypoglycemic range
 - Level 1 < 70mg/dL
 - Level 2 < 54 mg/dL
- Change from baseline in average daily number of units of bolus insulin dose
- Percent change from baseline in average daily insulin dose
- Achievement of a decrease of at least 0.3% in HbA1c at Week 12 (responders)

Additionally, analysis will be done on hypoglycemia both thresholds (54 mg/dl and 70 mg/dl) using the following variables:

- Change from baseline (2-week period) to Week 12 (2-week period) on the number of hypoglycemia episodes
- Proportion of patients with at least one more treatment-emergent episode of hypoglycemia at Week 12 (2-week period) relative to baseline (2-week period).
- Time-adjusted change from baseline on the number of hypoglycemia episodes.
- Proportion of patients with at least one more time-adjusted treatment-emergent episode of hypoglycemia at Week 12 than at baseline.

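### Within-arm paired tests are described as examining drug effects, but the Day 1 bolus insulin cut is not limited to one arm, so the insulin tests could be significant on placebo

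*SAP*

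**What the plan says.** SAP 7.6.2 states that secondary analysis of continuous measures will "examine drug effects within each treatment group using" a paired t-test and a one-sample Wilcoxon test. It adds: "Within each treatment group, the significance of the percent change from baseline will be assessed using a paired-t test", again with a Wilcoxon test in support. The same section also plans ANCOVA/ANOVA and MMRM for these endpoints.

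SAP 6.1.2 lists two insulin variables: "Change from baseline in average daily number of units of bolus insulin dose" and "Percent change from baseline in average daily insulin dose". The second is the only percent-change variable in SAP 6.1. SAP 1.3 repeats the wider protocol endpoint, which covers basal, bolus or total daily dose.

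Protocol 8.11, in the part covering Parts 1 and 2, gives this instruction for the first day of double-blind dosing: "Reduce bolus insulin". It has two steps: "INCREASE insulin to carb ratio (ICR, g/U) by 1-3 g/U (10-30%, usually 20" percent) and "INCREASE insulin sensitivity factor (ISF) by 10-30%, usually 20" percent. No arm is named, and Protocol 6.2 confirms that treatment is double-blind. During the first two weeks, and again afterwards, insulin is adjusted to glycemic targets, with bolus changes made through the same two ratios.

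Insulin is left alone during the run-in except for safety (Protocol 8.11). SAP 8.1 takes the insulin baseline from that run-in, and SAP 8.2 leaves Day 1 out of insulin calculations. The baseline therefore precedes the cut.

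**The concern.** A change from baseline in one arm measures everything that happened to that arm. On placebo it cannot be a drug effect, so the label in SAP 7.6.2 is wrong as written, whatever the data show.

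Insulin is where this matters most. The protocol itself directs a reduction at the moment treatment starts, in patients of both arms, and the baseline lies just before it. Lower mealtime insulin is also one of the benefits that the protocol synopsis sets out to look for. A significant within-arm fall on TTP399 could therefore be read as efficacy when part or all of it is the directed cut. A fall that is significant on TTP399 but not on placebo could be read as a difference between arms, which it does not show.

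**Working it through.** **Plan's own figures.** The documents give no figure for the within-arm insulin tests. The HbA1c sample size is not in dispute and reproduces: a difference of 0.7%, SD 1%, two-sided 0.049 and 80% power give 33 per arm by the normal formula, against 34 stated. Power at 34 is 0.82 (normal) or 0.81 (t).

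**Inputs.** 45 patients per arm (SAP 1.7); two-sided alpha 0.049 (SAP 7); insulin-to-carbohydrate ratio raised 10-30%, usually 20% (Protocol 8.11). The SD of percent change in insulin is not given, so 20-40% is assumed.

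**Step 1: size of the cut.** Carbohydrate bolus = grams / ratio. Raising the ratio by a fraction r changes the bolus by 1/(1+r) − 1.
- r = 0.10: −9.1%
- r = 0.20: −16.7%
- r = 0.30: −23.1%

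The correction bolus scales the same way with the sensitivity factor, for a given glucose excess.

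**Step 2: the test.** One-sample t-test with 44 degrees of freedom and critical value 2.025. It is significant once the observed mean change exceeds 2.025/√45 = 0.30 SD. The rejection probability comes from the noncentral t with noncentrality (mean/SD) × √45. For example, a 16.7% cut with SD 30% gives 16.67/30 × 6.708 = 3.73, and a rejection probability of 95.3%.

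**Step 3: chance that placebo is significant on percent change in bolus insulin** (20% rule, no drug effect):

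| Share of cut kept to Week 12 | SD 20% | SD 30% | SD 40% |
|---|---|---|---|
| All | 100% | 95% | 78% |
| Half | 78% | 44% | 27% |
| A quarter | 27% | 15% | 10% |
| None | 4.9% | 4.9% | 4.9% |

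With the whole cut kept and SD 30%, the 10% rule gives 51% and the 30% rule 99.9%.

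**Step 4: total daily insulin.** The Day 1 rule does not cut basal insulin. At an assumed 50% bolus share the full cut is 0.5 × 16.7 = 8.3% of the total. Placebo is then significant in 95%, 78% or 44% of trials at an SD of 15%, 20% or 30%. If half the cut is kept, these become 44%, 27% and 15%.

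**Step 5: within-arm against between-arm.** In 20,000 simulated trials with the same −16.7% shift in both arms, SD 30% and no drug effect, the within-arm placebo test rejects in 95.3%. A two-sample t-test between arms rejects in 4.9%, the nominal level. The shared shift cancels only in the between-arm comparison.

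**Step 6: significant in one arm only.** With half the cut kept in both arms and SD 30%, each arm is significant with probability 0.442. TTP399 is then significant while placebo is not in 0.442 × 0.558 = 25% of trials, with no drug effect at all.

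**The case against.** The Day 1 cut is a starting step. Protocol 8.11 then titrates insulin to target for low and for elevated glucose, and Protocol 7.3.8 repeats the review at the Week 4 and Week 8 calls. Placebo patients who need their former dose may be returned to it, and the last row of the table then applies. This stands: a reader might infer that placebo will show a significant insulin fall, but the documents support only that it could.

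A reader might also infer that the paired test is the only analysis of percent change in insulin. It is not. The general ANCOVA/ANOVA and MMRM rules in SAP 7.6.2 cover it, SAP 7.6.1 gives least-squares mean differences from placebo with 95% intervals, and Protocol 10.6.3 requires intervals for the difference between groups on secondary variables.

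Nor do the documents say that a within-arm p-value will support an efficacy claim. None of Evaluations 1-7 in SAP 2 uses one. SAP 2 names placebo added to standard insulin care as the control, and describes its confidence-interval look at insulin change as nominal. The primary conclusion is not exposed.

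What remains is that a prespecified significance test is described as examining drug effects, and the SAP nowhere calls it descriptive. A planned ANCOVA beside it does not correct that reading.

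**Conclusion.** The point holds as a flaw in the wording and interpretation of secondary analyses. A within-arm insulin change cannot isolate a drug effect in this trial, and on placebo it is not one.

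The size depends on how much of the Day 1 cut survives titration, which the documents do not predict, and on an SD that they do not give. For percent change in bolus insulin the placebo test ranges from the nominal 4.9% to nearly 100%. For total daily insulin, basal dilutes the effect. The figures assume 45 evaluable patients per arm, roughly normal percent changes, unchanged carbohydrate intake and use of the revised ratios. The hierarchy and the success rule are unaffected.

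**What to change.** In SAP 7.6.2:
- Remove the drug-effect wording, and either delete the within-group significance tests or label them descriptive.
- Report within-arm changes as means with confidence intervals.
- State that every drug-effect conclusion for a continuous secondary endpoint, explicitly including percent change in insulin, rests on the between-arm ANCOVA/MMRM difference with its confidence interval.

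The cost is SAP wording and fewer tests, with no new data or patients. No change to the insulin adjustment rule is proposed.

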7.6.3 Continuous Glucose Monitoring

Continuous glucose monitoring (CGM) data will be analyzed with the following categories of interest:

- Level 2 hypoglycemia: < 54 mg/dl
- Level 1 hypoglycemia: < 70 mg/dl
- Normal or target: in the range 70-180 mg/dl
- Level 1 hyperglycemia: > 180 mg/dl
- Level 2 hyperglycemia: > 250 mg/dl

Supportive analysis will be done on the endpoint percentages of subjects in the target range or outside of the range by level.

Additionally, non-overlapping categories will be examined:

- Level 2 hypoglycemia: < 54 mg/dl
- Level 1 hypoglycemia: between 54 (inclusive) and 70 (not inclusive) mg/dl
- Normal or target: in the range 70-180 mg/dl
- Level 1 hyperglycemia: > between 180 (not inclusive) and 250 (inclusive) mg/dl
- Level 2 hyperglycemia: > 250 mg/dl

Average daily glucose at endpoint and change in average daily glucose will also be done as supportive analysis. The comprehensive analysis will also include standard deviation and CV.

7.6.3.1 Daytime analysis for Continuous Glucose Monitoring

There is particular interest in the effects of treatment with TTP399 on CGM during daytime hours when subjects are awake, eating, and moving. For purposes of analysis of daytime and nighttime (for completeness), the definitions of daytime and nighttime will be as follows:

- Daytime: 6am to 10pm (inclusive)

- Nighttime: 10pm to 6am (not inclusive).

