It is noted that strict application of the Hochberg methodology implies that rigorous p-values may not be applicable in the event of failure to reject either hypothesis in Evaluation 2. The intersection hypothesis is, however, applicable, and it is the intention of this analysis plan to continue testing under the intersection hypothesis and interpret p-values as rigorous as opposed to nominal.

Superiority on treatment response is evaluated:

- H_{02} : The proportion of treatment responders at Week 12 for the group treated with 800 mg TTP399 is equal to that of the placebo group.
- H_{12} : The proportion of treatment responders at Week 12 for the group treated with 800 mg TTP399 is not equal to that of the placebo group.

The study is declared to have met its primary endpoint if Evaluation 1 concludes TTP399 plus the modified regimen of insulin is noninferior to optimized insulin

And

Using the Hochberg method, either Evaluation 2 finds TTP399 is superior on HbA1c or Evaluation 3 finds TTP399 is superior on the proportion of treatment responders.

Conditional on achievement of endpoints, statistical evaluation continues.

Conditional Second Statistical Evaluation:

- **Evaluation 4:**

Superiority on daytime time in range is evaluated:

- H_{03} : The mean change in daytime time in range from baseline to Week 12 for the group treated with 800 mg TTP399 is equal to that of the placebo group.
- H_{13} : The mean change in daytime time in range from baseline to Week 12 for the group treated with 800 mg TTP399 is not equal to that of the placebo group.

Conditional Third Statistical Evaluation:

- **Evaluation 5:**

Superiority on time in hypoglycemia using 70 mg/dl as the threshold is evaluated:

- H_{04} : The mean change in time in hypoglycemia using 70 mg/dl as the threshold from baseline to Week 12 for the group treated with 800 mg TTP399 is equal to that of the placebo group.
- H_{14} : The mean change in time in hypoglycemia using 70 mg/dl as the threshold from baseline to Week 12 for the group treated with 800 mg TTP399 is not equal to that of the placebo group.

Conditional Fourth Statistical Evaluation:

- **Evaluation 6:**

Superiority on time in hypoglycemia using 54 mg/dl as the threshold is evaluated:

- H_{05} : The mean change in time in hypoglycemia using 54 mg/dl as the threshold from baseline to Week 12 for the group treated with 800 mg TTP399 is equal to that of the placebo group.

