8.2 Continuous Glucose Monitoring and insulin conventions

Continuous glucose monitoring (CGM) measures are automated by device. Insulin data are collected from InPen or pump devices (some of which is keyed) and curated by qualified data managers. It is noted that prescribed insulin is used for basal insulin, and recorded insulin is used for bolus.

Gaps may occur in either parameter. The following conventions will be used:

- There must be at least 10 days of data available to support any period calculation of summary statistics.
- Day 1 and Day 84 will not be used in any calculation of CGM or insulin.
- Other visit days will not be used, due to potential disruptions and likely gaps. An important note is that all CGM data will be included in the evaluation of hypoglycemia events.
- Data from shift workers (individuals who work outside of normal business hours) will not be used for CGM.
- Insulin data from days with pump failure will not be used.
- If there is a gap in the measure of more than 8 hours, the 24-hour period will not be used.
- If < 80% of the data are available, the measure will not be used.
- If blind review (done in accordance with ICH E9 guidance) identifies a gap for which inclusion of the day could be misleading, the day will not be used.
- If a glucose value exceeds 400 mg/dl, the event is examined blinded to treatment for evidence of significant deviation from the prescribed insulin regimen, and if blind review determines that there is likely significant deviation from the prescribed insulin regimen, the days CGM and insulin data will not be used.
- Device manufacturers for CGM have researched and documented that improvements in HbA1c as much as 1% can be observed within 3 months of beginning use of the CGM device. In this subject population in consideration for the mechanism of action for GKA, it is unexpected for a subject to experience changes in HbA1c of more than 1% in either direction. Any observed change of more than 1% will be queried to determine whether or not the use of the CGM began with the initiation of the study or whether there is some other medical explanation from the principal investigator that may reveal a major protocol deviation or a dramatic change that is not interpretable for protocol purposes. Blind review (done in accordance with ICH E9 guidance) will evaluate protocol suitability of the data, if there are explanations disallowed by the protocol; such

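### CGM day completeness is judged on the 24-hour period, but Evaluation 4 tests a 6am-10pm endpoint, so usable daytimes can be dropped and thin ones kept

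*SAP*

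**What the plan says.** SAP section 2, Evaluation 4, is the first CGM hypothesis in the conditional testing sequence: "Superiority on daytime time in range is evaluated". SAP 7.6.3.1 defines the windows as "Daytime: 6am to 10pm (inclusive") and "Nighttime: 10pm to 6am (not inclusive"), that is, 16 and 8 hours. It explains that the daytime window is of interest because patients are then awake, eating and moving.

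SAP 8.2 sets the completeness conventions for CGM and insulin together:

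- Gap rule: "If there is a gap in the measure of more than 8 hours, the 24-hour period will not be used".
- Availability rule: "If < 80% of the data are available, the measure will not be used". It does not say 80% of what.
- Minimum days: "There must be at least 10 days of data available to support any period calculation of summary statistics".
- Visit days: Day 1 and Day 84 are excluded, and "Other visit days will not be used, due to potential disruptions and likely gaps".
- Blinded review: if it "identifies a gap for which inclusion of the day could be misleading, the day will not be used". No numeric criterion is attached.

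No rule is written for the daytime window. The term 24-hour period is not defined as a calendar date or otherwise.

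Protocol 7.3.5 and 7.3.10 require at least 13 days between the visits that open and close each sponsor CGM period. SAP 7.5 assigns missing measures to multiple imputation.

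**The concern.** The only explicit day-level rule looks at all 24 hours, while the endpoint uses 16 of them. A day can therefore be lost because of hours that Evaluation 4 does not use. Depending on what the 80% refers to, a day can also be kept although a large share of the waking, mealtime hours is missing.

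The margin for lost days is thin. Visit days are already excluded, and SAP 8.2 also removes certain holidays and some days with glucose above 400 mg/dL. A few further losses take a period below 10 days. At stake are the precision of daytime time in range and how well it represents the hours it is meant to describe. Evaluation 4 also stands ahead of the two hypoglycemia tests and the quality-of-life test in the conditional sequence.

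**Working it through.** The SAP gives no completeness, power or SD figure for daytime time in range, so there is no stated figure to reproduce.

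**Inputs.** Daytime 16 h and night 8 h (SAP 7.6.3.1). Gap limit more than 8 h, 80% rule, 10-day minimum, visit days excluded (SAP 8.2). Interval at least 13 days (protocol 7.3.5, 7.3.10).

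**Step 1: the gap rule alone.** Night is exactly 8 h and the rule needs more than 8 h, so a gap confined to the night never triggers it. A gap that spills a little into daytime does:

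- Midnight to 8:30am is 8.5 h, so the day is deleted. Daytime lost is 2.5 h; observed is 13.5/16 = 84%.
- 9:45pm to 6am is 8.25 h. If the 24-hour period is not a calendar date, the day is deleted with 15.75/16 = 98% of daytime observed. If it is a calendar date, the gap splits into 2.25 h and 6 h and nothing is deleted.

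A single gap of exactly 8 h inside daytime passes, with 8/16 = 50% observed.

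**Step 2: add the 80% rule under each reading.**

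| 80% of what | Night-only gap that deletes a complete daytime | Most daytime a single gap can remove on a kept day |
|---|---|---|
| 24-hour day | over 0.2 x 24 = 4.8 h | 4.8/16 = 30% |
| Whole period | none at day level | 8/16 = 50%, unless blinded review removes the day |
| Daytime measure | none | 0.2 x 16 = 3.2 h, or 20% |

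Under the 24-hour-day reading an 8-h gap leaves 16/24 = 67%, so the gap rule adds nothing. Under the period reading, 12 days give 288 h with 57.6 h allowed missing. Since 57.6/8 = 7.2, up to 7 of 12 days could each carry an 8-h daytime gap. Under the daytime reading the midnight to 8:30am day passes the 80% rule (84%) and is still deleted by the gap rule. Some mismatch therefore remains under every reading.

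**Step 3: consequence for the period.** A 13-day interval leaves 13 - 1 = 12 non-visit days. Losing three leaves 9, below 10, and the period becomes missing. A 14-day interval leaves 13 days, so four must be lost.

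**Step 4: how often.** The documents give no gap frequency. As an assumption, let each day fail independently, from any cause, with probability q. With n days, the period is usable with probability P(n, q) = P(at least 10 of n days valid), and at least one of the two periods fails with probability 1 - P(n, q)^2.

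| n | q | P(n, q) | at least one period fails |
|---|---|---|---|
| 12 | 5% | 0.980 | 4% |
| 12 | 10% | 0.889 | 21% |
| 13 | 5% | 0.997 | 0.6% |
| 13 | 10% | 0.966 | 7% |

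**The case against.** A reader might infer that the plan deletes complete daytimes for night gaps and, at the same time, counts half-empty ones. The documents do not support that at day level. A complete daytime is deleted for a night-only gap only if 80% is per 24-hour day, and that reading also removes half-empty daytimes. If 80% is per period, half-observed daytimes can survive, but a deleting gap must reach into daytime, so the day lost is nearly complete at most. This limits the point but does not remove it.

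The 80% bullet speaks of the measure. Applied to daytime time in range it could already mean 80% of daytime data. That is a fair reading, but it is not stated, and the 24-hour gap rule would still apply beside it.

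Blinded review can drop a day with a misleading gap. This is a real safeguard against thin daytimes. It is discretionary, and nothing in SAP 8.2 lets it restore a day already deleted by rule.

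A reader might also infer that a patient with too few days leaves Evaluation 4. The plan does not say so. Full analysis set membership depends on HbA1c (SAP 4, 7.6.1), and a missing measure goes to multiple imputation (SAP 7.5), with observed-cases and LOCF approaches also named in SAP 7.6.2. The recorded daytime data are nevertheless set aside.

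Finally, one common set of valid days for daytime, night and 24-hour measures is a defensible preference. It is a matter of convenience, and it comes at the cost of usable daytime data.

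**Conclusion.** The point holds as a mismatch between the completeness window and the endpoint window, together with an unstated denominator. Depending on the reading, the plan can delete days with 84% to 100% of daytime observed, and can keep days missing 20%, 30% or 50% of it.

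The practical size is unknown. The range of 0.6% to 21% of patients losing at least one period rests on assumed independent daily failure of 5% to 10% and on 12 or 13 available days. It counts failure from any cause, so it does not measure the share due to night gaps or the share that the fix would rescue. The 21% is the upper corner of that range, at the minimum interval, and should not be read as an expected loss.

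A reader might also infer bias in the treatment comparison. None is shown: the rules apply to both arms alike, the review is blinded, and the documents offer no mechanism that differs by arm. HbA1c and its sample size are unaffected. This is a cheap improvement, not a flaw in the primary analysis.

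**What to change.** In SAP 8.2, for CGM:

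- For daytime measures, judge each day on 6am-10pm only, for example at least 80%, or 12.8 of 16 h, in place of the 24-hour gap rule. Count the 10 days on that basis.
- For night and 24-hour measures, use the matching window (at 80%: 6.4 of 8 h and 19.2 of 24 h).
- State that the 80% rule is per day.

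Daytime loss on a counted day is then capped at 3.2 h (20%), and no night-only gap can remove a daytime. The blinded gap review can stay as it is.

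The cost is a few lines of SAP text and one derivation, to be settled before unblinding. The downside is that the set of valid days will differ slightly between daytime and 24-hour endpoints, which should be noted in the tables.
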